In spite of the encouraging efficacy of HMA with venetoclax in newly diagnosed older AML who are not good candidates for cytotoxic induction therapy, the median CR/CRI durations are $\leq 11-12$ months and median 3-year OS is $<45\%$ (DiNardo CD et al, *Blood*. 2019 Jan 3;133(1):7-17) suggesting that there is room for improvement by further improving the durability of CR/CRI's and thereby improving median OS. Similarly, MRD-negative rates with HMA with venetoclax are 40-50% and these may be further improved by the addition of an effective and tolerable third agent, potentially translating into more durable response and improved OS.

The long-term outcomes of patients with poor-risk disease features remain poor. Among frontline older poor risk patients treated with HMA with venetoclax (defined as patients with TP53 and adverse cytogenetics) evaluated in both the MDACC internal data set (Shoukier M et al, *Journal of Clinical Oncology* 37, no. 15_suppl (May 20, 2019) 7034-7034) and in the multicenter phase Ib/II trial of HMA with venetoclax (DiNardo CD et al, *Blood*. 2019 Jan 3;133(1):7-17) the

CR/CRi rates were significantly lower at 45-47%, median response durations were <6 months, median OS was 6-9 months, and only 14% of the patients achieving CR/CRi became MRD-negative.

Venetoclax plus HMA in R/R AML: Several retrospective studies have been published evaluating the safety and efficacy of venetoclax plus an HMA in patients with R/R AML.

-A study from MD Anderson evaluated the outcomes of 43 patients with R/R myeloid malignancies (n=39, 91% with AML) who received venetoclax in combination with other agents (DiNardo CD et al, *American journal of hematology* 2018; **93**(3): 401-7). Thirty-one of the evaluated patients (72%) received venetoclax with an HMA. Most patients (84%) were treated in salvage 2 or later (range 2-8) with a median of 3 prior treatment regimens. Objective response rate (ORR) was achieved in 9 (21%) patients, including 2 (5%) with CR, 3 (7%) with CRi, and 4 (9%) with morphologic leukemia-free state (MLFS). Of the 9 responding patients, all responded within 1 cycle of venetoclax combination therapy. These nine responding patients included eight (26%) of the patients treated with an HMA combination. With a median follow-up of 3 months, the estimated 6-month OS rate was 24% and median OS was approximately 5 months.

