-In another study of venetoclax in combination with HMAs in R/R AML from City of Hope, 33 patients were treated (Aldoss I et al, *Haematologica*. 2018 Sep; **103**(9):e404-e40). The median number of prior therapies was 2 (range, 1-8). Twenty patients (61%) had failed HMA therapy previously and 13 patients (39%) had prior allogenic stem cell transplantation. The ORR was 64% (N=21), with 10 patients (30%) achieving CR, 7 (21%) achieving CRi and 4 (12%) achieving MLFS. With a median follow-up of 6.5 months, the 1-year OS rate was 53%.

-The group at Memorial Sloan Kettering Cancer Center has also reported their experience with venetoclax in combination with either low-dose cytarabine or an HMA in patients with R/R myeloid malignancies (Goldberg A et al, *Blood* 2017; **130**(Suppl 1): 1353). A total of 24 patients were treated (n=8 with HMA; N=16 with low-dose cytarabine). Twenty-three patients (96%) had a diagnosis of AML. The median number of prior treatments was 3 (range, 1-8); 6 patients (29%) had prior stem cell transplantation. Of 21 patients evaluable for efficacy, the ORR was 29%, including a CR rate of 24% (n=5) and PR rate of 5% (n=1). With a median follow-up of 4.1 months, the 3-month OS rate was 72%.

Pre-clinical rationale for combination of venetoclax with immune therapies

In a series of human *in vitro* and *in vivo* syngeneic tumor model studies, venetoclax does not appear to antagonize anti-PD-1 therapy with nivolumab (Mathew R et al. *Blood* 2018 132: 3704). Venetoclax was shown to decrease naïve T-cells and B-cells but not central and effector memory T cells (these being critical to anti-tumor immunity) in *in vitro* studies of human lymphocytes. In a mixed lymphocyte reaction assay, venetoclax did not affect IFN-gamma secretion from CD3/CD28

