4.2 Inclusion Criteria

4.2.1 **A. Arm 1 Salvage cohort:** Patients with AML or biphenotypic or bilineage leukemia who have failed prior therapy. Patients with AML should have failed prior therapy or have relapsed after prior therapy will be eligible for Arm 1.

B. Arm 2 and 3 Salvage cohorts: Patients with AML who have failed up to two prior therapeutic regimens (i.e. salvage 1 or 2 status) will be eligible for Arm 2 relapse cohort. Allogeneic stem cell transplant for patients in remission at the time of stem cell transplant will not be considered a salvage regimen. Similarly, hydroxyurea if used alone will not be considered a salvage regimen.

During the lead-in phase (part a) of Arm 3, see Table 5C below, only R/R AML patients who meet the “Salvage cohorts” criteria will be enrolled.

C. Arm 1, 2 and 3 Frontline cohorts: Not considered candidates for intensive remission induction chemotherapy at time of enrollment based on EITHER:

A. ≥ 75 years of age OR

B. <75 years of age with at least 1 of the following:

-Poor performance status (ECOG) score of 2-3.

-Clinically significant heart or lung comorbidities, as reflected by at least 1 of:

a. Left ventricular ejection fraction (LVEF) $\leq 50\%$.

b. Lung diffusing capacity for carbon monoxide (DLCO) $\leq 65\%$ of expected.

c. Forced expiratory volume in 1 second (FEV1) $\leq 65\%$ of expected.

d. Chronic stable angina or congestive heart failure controlled with medication.

-Liver transaminases $>3 \times$ upper limit of normal (ULN).

-Other contraindication(s) to anthracycline therapy (must be documented).

-Other comorbidity the investigator judges incompatible with intensive remission induction chemotherapy, which must be documented and approved by the PI.

Patients with newly diagnosed AML with poor risk karyotype or complex karyotype and/or TP53 deletions/mutations equal or younger than 60 year old will be eligible for the Frontline cohort as well.

4.2.2 Patients with MDS or CMML who received therapy for the MDS or CMML and progress to AML are eligible at the time of diagnosis of AML regardless any prior therapy for MDS or CMML. The WHO

classification will be used for AML. Prior therapy for MDS or CMML will not be considered as a prior therapy for AML, hence such patients will be considered as frontline AML and eligible for the frontline elderly cohort.

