E. Arm 3 First and Second Salvage AML cohort (AZA + VEN + Nivo) (N=30)

Historical data for salvage patients with azacitidine and venetoclax show an overall response rate (ORR) of 25-50% (DiNardo CD et al, *American journal of hematology* 2018; **93**(3): 401-7; Aldoss I et al, *Haematologica*. 2018 Sep;103(9):e404-e40; Goldberg A et al, *Blood* 2017; **130**(Suppl 1): 1353). It is expected for the current trial that the three-drug combination will improve the ORR by 35% while the toxicity rate is maintained at or below 30%. A sample size of 30 patients ensures that, if the trial is not terminated early, a posterior 90% credible interval for ORR will have width of 0.28 at most, under the assumption of a 60% of ORR rate. The prior probabilities of ORR and toxicity for the experimental regimen are modeled by beta distributions (*Beta* (0.5, 1.5) and *Beta* (0.6, 1.4), respectively). Denoting the historical proportion of overall response rate and toxicity rate by $\{p(\text{ORR},H) = 25\%, p(\text{TOX},H) = 30\%\}$, the following decision criteria will be applied:

- 1) Stop if $\text{Prob}\{p(\text{ORR},H) + \delta_{\text{OR}} > p(\text{ORR},E) \mid \text{data}\} > 0.975$, where $\delta_{\text{OR}} = 0.35$
- 2) Stop if $\text{Prob}\{p(\text{TOX},H) + \delta_{\text{TOX}} < p(\text{TOX},E) \mid \text{data}\} > 0.95$, where $\delta_{\text{TOX}} = 0$

Patients will be monitored in cohorts of 5 according to the following stopping boundaries for overall response and DLT.

| # Patients Evaluated | Stop if this cohort ≤ this # ORR | Stop if ≥ this # toxicities |
|----------------------|-------------------------------------|-------------------------------------|
| 5 | 0-1 | 4-5 |
| 10 | 0-3 | 6-10 |
| 15 | 0-5 | 8-15 |
| 20 | 0-8 | 10-20 |
| 25 | 0-10 | 12-25 |
| 30 | Always stop with this many patients | Always stop with this many patients |

The operating characteristics are summarized in the following table (based on simulations from 10,000 trials).

| True Toxicity Rate | True ORR Rate | PROB(Stop Early) |
|--------------------|---------------|------------------|
| 0.10 | 0.25 | 0.9838 |
| | 0.45 | 0.5615 |
| | 0.60 | 0.1459 |
| | 0.75 | 0.0185 |
| | 0.90 | 0.0011 |
| 0.20 | 0.25 | 0.9840 |
| | 0.45 | 0.5676 |
| | 0.60 | 0.1579 |
| | 0.75 | 0.0322 |
| | 0.90 | 0.0150 |
| 0.30 | 0.25 | 0.9856 |
| | 0.45 | 0.6094 |
| | 0.60 | 0.2393 |
| | 0.75 | 0.1258 |
| | 0.90 | 0.1102 |
| 0.40 | 0.25 | 0.9900 |
| | 0.45 | 0.7297 |
| | 0.60 | 0.4736 |
| | 0.75 | 0.3951 |

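### The Arm 3 salvage benchmark understates the upper end of its own cited series (50% against 64%), so neither the 35-point gain nor an ORR near 60% shows improvement over azacitidine-venetoclax

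*Combined protocol and SAP*

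**What the plan says.** Section 11.3 E (Arm 3, first and second salvage) cites three published series and summarises them: "Historical data for salvage patients with azacitidine and venetoclax show an overall response rate (ORR) of 25-50" per cent. It sets p(ORR,H) at 25% and expects the triplet to "improve the ORR by 35% while the toxicity rate is maintained at or below 30" per cent. The futility rule therefore compares the triplet with 0.25 + 0.35 = 0.60. The priors are "modeled by beta distributions (*Beta* (0.5, 1.5) and *Beta* (0.6, 1.4), respectively". The sample size of 30 is justified by precision: "a posterior 90% credible interval for ORR will have width of 0.28 at most, under the assumption of a 60% of ORR rate".

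Section 2.3 E describes the same three series. In the first, 9 of 43 patients responded (21%), including 8 of the 31 on an HMA combination (26%). On pretreatment it says: "Most patients (84%) were treated in salvage 2 or later (range 2-8) with a median of 3 prior treatment regimens". The second series, 33 patients all given venetoclax with an HMA, had a median of 2 prior therapies (range 1-8): "The ORR was 64% (N=21), with 10 patients (30%) achieving CR, 7 (21%) achieving CRi and 4 (12%) achieving MLFS". In the third, 16 of 24 treated patients received low-dose cytarabine and 8 an HMA. Its ORR was 29% of 21 evaluable (5 CR, 1 PR), with a median of 3 prior treatments (range 1-8).

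Section 4.2.1 B limits the cohort: "Patients with AML who have failed up to two prior therapeutic regimens". Section 11.2 defines the Arm 3 ORR as CR + CRp + CRi + MLFS within 6 months.

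**The concern.** The benchmark range does not match the plan's own account of its sources. The second series is the only one made up wholly of HMA-venetoclax patients, and it scores response almost exactly as Arm 3 does. Its 64% lies outside the stated range and above the triplet's 60% target.

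The choice of 25% matters too. In the four Arm 1 and Arm 2 cohorts the historical rate is the top of the quoted range (15% from 10-15% and from 12-15%; 25% from 18-25% twice). Arm 3 salvage alone uses the bottom, and no reason is given.

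The two lower series had a median of 3 prior regimens, while this cohort admits at most two. So 25% probably understates what the doublet would achieve in the patients enrolled. At stake is how a good-looking result is read: 60% would appear to be a large gain over azacitidine-venetoclax when the doublet might give much the same rate.

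**Working it through.** **1. Reproduce the plan's figures.** Inputs (11.3 E): ORR prior Beta(0.5, 1.5); stop if P(p < 0.60 | data) > 0.975; toxicity prior Beta(0.6, 1.4); stop if P(p > 0.30 | data) > 0.95; looks at 5, 10, 15, 20 and 25 patients.

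With x responders among n, the posterior is Beta(0.5 + x, 1.5 + n - x). At n = 25, x = 10 gives P(p < 0.60) = 0.987 (stop) and x = 11 gives 0.966 (continue), so the limit is 10, as printed. All five futility limits (1, 3, 5, 8, 10) and all five toxicity limits (4, 6, 8, 10, 12) reproduce.

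An exact look-by-look binomial recursion, with response and toxicity independent, matches all 25 printed operating characteristics. For example, at toxicity 0.10 the early-stop probability is 0.9838, 0.5615 and 0.1459 for ORR 0.25, 0.45 and 0.60. At 18/30 the 90% credible interval is 0.434 to 0.717, width 0.283, which rounds to the stated 0.28. The calculations are sound; the input is the problem.

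**2. Restate the benchmark from section 2.3 E.**

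| Series | HMA-venetoclax result | Exact 95% CI | Median prior regimens |
|---|---|---|---|
| First | 8/31 = 26% | 12-45% | 3 (whole series) |
| Second | 21/33 = 64% | 45-80% | 2 |
| Third | not reported separately | - | 3 (whole series) |

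The HMA-venetoclax range is 26-64%. The upper end is 64 - 50 = 14 points above the stated one. Pooling HMA patients with reported counts gives (8 + 21)/(31 + 33) = 29/64 = 45%.

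The stated 50% is close to CR + CRi alone in the second series, (10 + 7)/33 = 52%, but Arm 3 also counts MLFS, which makes 64% the matching figure. The study rationale (section 2.6) gives yet another range for these three citations, 20-40% for CR/CRp/CRi, which 52% also exceeds.

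The 60% target is 60 - 25 = 35 points above the plan's anchor, 15 above 45%, 10 above 50%, and 4 below 64%.

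**3. What happens if nivolumab adds nothing.** Set the triplet's true ORR equal to the doublet rate and apply the printed boundaries. The chance of no toxicity stop is 0.9994 at true toxicity 0.10 and 0.890 at 0.30. Multiplying by the response-side probabilities gives the ranges.

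| Doublet rate | No futility stop | Completes accrual (toxicity 0.10-0.30) | No futility stop and at least 18/30 | Completes with at least 18/30 (toxicity 0.10-0.30) |
|---|---|---|---|---|
| 25% | 0.016 | 1-2% | < 0.001 | < 0.1% |
| 45% | 0.439 | 39-44% | 0.067 | 6-7% |
| 50% | 0.607 | 54-61% | 0.170 | 15-17% |
| 64% | 0.911 | 81-91% | 0.717 | 64-72% |

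Example at 50%: 0.607 x 0.890 = 0.54 and 0.170 x 0.890 = 0.15.

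**4. What 18/30 could separate.** Its exact 95% CI is 41-77%, which contains 45%, 50% and 64%. Fisher's exact p is 0.80 against 21/33, 0.27 against 29/64 and 0.010 against 8/31. The result would stand apart from the low series only.

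**The case against.** The strongest reply is that the plan claims less than this criticism assumes. Objective 5 is to determine the ORR, and the analysis plan estimates it with a 95% CI, without a test against history. The design is openly non-randomised, so attribution to nivolumab was never on offer. Only the sum 0.60 drives the futility rule; splitting it differently between benchmark and gain changes no boundary. All of this stands, and it is why the boundaries and sample size need no change. It does not excuse a reference range that contradicts its own citations, or an expected gain built on that range.

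Several stronger readings are tempting and are not supported:

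- A reader might infer that the lower bound is also wrong, because the first series is 21% overall. That figure includes 12 patients not on an HMA; the relevant 26% agrees with 25%.
- A reader might pool all three series to 36/97 = 37%. That mixes backbones and counts a PR, which Arm 3 excludes.
- A reader might take completion probabilities as chances of reaching the target. The rule can let a cohort finish with 11/30, so the two must be kept apart: at a 50% doublet rate they are 54-61% and 15-17%.
- A reader might say the table hides the risk. Its 0.45 and 0.60 rows already imply 39-44% and 76-85% completion at toxicity 0.10-0.30.
- A reader might treat 64% as the true doublet rate. It comes from 33 patients, some with up to 8 prior therapies; 61% had failed an HMA and 39% had a prior transplant.
- The 84% treated in salvage 2 or later does not show ineligibility, since salvage 2 is admitted. The median of 3 is what lies outside the cap, and the series may count regimens differently from this protocol.

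**Conclusion.** Wrong as written, at the upper end of the range. The plan's own sources support 26-64% for HMA-venetoclax, not 25-50%, and one doublet series exceeds the triplet's target. The 35-point improvement depends on taking the bottom of the range, from series that were more heavily pretreated on median. The doublet rate in this cohort is probably above 25%, but the documents do not allow the difference to be estimated.

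The practical size depends on that unknown rate. With no nivolumab effect, the chance of finishing at 18/30 or better is negligible at 25%, modest at 45-50% (6-17%) and high at 64% (64-72%). These figures assume independent response and toxicity, true toxicity of 0.10-0.30 and the printed boundaries. It does not follow that nivolumab is inactive, or that 60% would be uninformative against a 25% rate. What follows is that completing accrual, or an ORR near 60%, is not by itself evidence of improvement over azacitidine-venetoclax.

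**What to change.** In section 11.3 E:

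1. Restate the historical ORR as 26-64% for HMA-venetoclax, giving for each series the denominator, backbone, response definition and number of prior regimens. Describe the third series separately as mainly low-dose cytarabine with PR counted.
2. Replace the 35-point improvement with a statement that 0.60 is the futility reference rate, and that completing accrual or an ORR near 60% is not by itself evidence of improvement over azacitidine-venetoclax.
3. Add operating-characteristic rows at true ORR 0.50 (early stop 0.394, 0.402 and 0.460 at toxicity 0.10, 0.20 and 0.30) and 0.64 (0.090, 0.102 and 0.189). The 0.45 row is already printed. Do not add a row for the mixed 37% pool.
4. In the analysis plan, tabulate Arm 3 salvage ORR by number of prior regimens, which eligibility screening already requires to be known.

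The boundaries and n=30 stay as they are. The cost is wording, two table rows and one extra table; the downside is that the stated expected gain looks less favourable.

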| Median cycles to response | 2 [1 – 13] | 2 [1 – 9] | 2 [1 – 6] |
| Median follow up, in months | 27.2 [21.7 – 35.1] | 11.8 [| 51 [0.1 – 64.8] |
| 4 weeks mortality | 3 (4) | 0 | 12 (7) |
| 8 weeks mortality | 10 (14) | 2 (8) | 34 (20) |

Abbreviations: N, number, CR, complete remission, CRi, complete remission with incomplete count recovery, PR, partial response, HI, hematologic improvement

*Hematologic improvement in one or more parameter maintained >6 months on study

[@]Stable disease (SD) was defined as the absence of CR, CRi, PR, MLFS, HI without evidence of clinical deterioration or proliferative disease, maintained >6 months on study. This particular response was not captured for control.

2.3 E

Venetoclax in AML (Background and unmet need)

--Venetoclax plus HMA in patients with newly diagnosed AML

An ongoing phase Ib/II study has reported promising safety and efficacy of venetoclax in combination with either azacitidine or decitabine in patients ≥ 65 years of age with previously untreated AML and who are ineligible for chemotherapy (DiNardo CD et al, *Blood*. 2019 Jan 3;133(1):7-17). At the most recent update (Pollyea D et al ASH 2018 Oral presentation Abstract 285: full PowerPoint attached as Appendix), 145 patients were treated with a median age of 74 years (range, 65-86 years). Cytogenetics were poor risk in 49% of patients. The 30-day and 60-day mortality rates were 3% and 8%, respectively. Tumor lysis syndrome was not observed. The CR/CRI rate for the entire cohort was 66% with a median duration of CR/CRI of 11.0 months. The median overall survival for the entire cohort was 17.5 months. These results represent the best survival data for older, unfit patients reported to date in newly diagnosed AML. Based on these exciting results in this historically difficult-to-treat patient population, in November 2018 the US FDA approved venetoclax in combination with either LDAC, azacitidine or decitabine for patients with newly diagnosed AML who are ≥ 75 years of age or have comorbidities that preclude the use of standard intensive chemotherapy.

Emerging clinical and exposure response data have suggested that the 400mg dose of venetoclax has the best risk-benefit profile, and a phase III study of venetoclax 400mg with azacitidine in the frontline setting is ongoing and has recently completed enrollment (VIALE A).

--Unmet Need in AML and Need to Continue Improving HMA with Venetoclax

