Clinical Efficacy Data for Venetoclax: Preliminary efficacy results are available for subjects with a variety of hematological neoplasms; the drug is approved for the treatment of CLL patients whose cells have a 17p chromosomal deletion. Preliminary data indicate that venetoclax shows promising efficacy in AML.

- In Study M14-212 the CR/CRi rate for subjects treated with venetoclax monotherapy was 19% (Konopleva M et al, *Cancer discovery* 2016; **6**(10): 1106-17).
- In Study M14-358 the CR/CRi rate for AML subjects (given venetoclax plus azacitidine or decitabine) was 66% (DiNardo CD et al, *Blood*. 2019 Jan 3;133(1):7-17).
- In Study M14-387 the CR/CRi rate for AML subjects (given venetoclax plus low dose ara-C) was 54% (Wei A et al [J Clin Oncol.](#) 2019 May

Venetoclax Clinical Pharmacology and Pharmacokinetics: Venetoclax clinical pharmacology is being evaluated in several Phase I to III clinical trials, and data are available from three Phase I studies (M12-175, M13-367, M12-630), four Phase Ib studies (M13-365, M12-901, GO29440, GP28331), one Phase II study (M14-212) and five dedicated clinical pharmacology studies (Study M13-364, M14-497, M13-363, M14-253 and M15-101).

In the Phase 1 Study M14-358, preliminary pharmacokinetic results in 31 treatment-naïve AML subjects were available for venetoclax doses ranging from 400 mg to 800 mg when given in combination with decitabine (Arm A) or azacitidine (Arm B) and with or without posaconazole (Arm C). For Arm A and Arm B, venetoclax steady-state mean Cmax and AUC24 (Cycle 2 Day 5) ranged from 1.77 – 3.36 µg/mL and 24.7 – 59.5 µg/mL, respectively. Based on the limited preliminary pharmacokinetic data, there was no evidence to suggest a marked effect of the co-administration of decitabine and azacitidine on the pharmacokinetics of venetoclax. In Arm C of this study, preliminary pharmacokinetic results from 6 subjects were available on Cycle 1 Day 20 (venetoclax 400 mg alone QD until Day 20) and Cycle 1 Day 28 (venetoclax 100 mg QD with posaconazole given from Day 21 to Day 28). Venetoclax Cmax and AUC following co-administration of venetoclax 100 mg with posaconazole were 2.1- and 2.7-fold higher respectively, compared to venetoclax 400 mg alone.

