Two ongoing trials are evaluating VEN combination regimens in treatment naïve patients with AML who are ≥ 65 years of age and who are not eligible for standard induction: (a) to evaluate the efficacy and tolerability of the combination of VEN with a methyltransferase inhibitor (azacytidine or decitabine) (ClinicalTrials.gov Identifier: NCT02203773); (b) to evaluate VEN with low-dose cytarabine (ClinicalTrials.gov Identifier: NCT02287233).

Overview of Ongoing Phase 1b Study (M14-358): Venetoclax in Combination with HMA in Treatment Naïve AML

As of 09 March 2016, a total of 45 subjects ≥ 65 years of age with treatment naïve AML ineligible to receive standard induction therapy were enrolled into the escalation stage at 3 dose levels of venetoclax at 400 mg, 800 mg, and 1200 mg. Venetoclax was administered daily during the 28-day cycles in combination with decitabine (20 mg/m^2 intravenously on Days 1 – 5 once every 28 days) or azacitidine (75 mg/m^2 intravenously or subcutaneously on Days 1 – 7 once every 28 days). Preliminary safety and efficacy data are available from the ongoing dose escalation stage of this trial.

The most common adverse events for all subjects in Study M14-358 were nausea (53.3%), diarrhea (44.4%), febrile neutropenia (40.0%), neutrophil count decreased (31.1%), platelet count decreased, cough, and fatigue (28.9% each), edema peripheral and hypokalemia (26.7% each). Events grade 3 and above were reported for the majority (91.1%) of subjects; the most common event was febrile neutropenia (40.0%). Serious adverse events were reported for 27 (60.0%) subjects, including febrile neutropenia (11 subjects), malignant neoplasm progression (3 subjects) atrial fibrillation, abdominal pain, non-cardiac chest pain, pyrexia, pneumonia, sepsis, bone pain (2 subjects each). All other events occurred in 1 subject each. The combination of venetoclax with decitabine and azacitidine demonstrates a tolerable safety profile.

As of 09 March 2016, the ORR, as assessed by the investigators for the subjects enrolled into the 3 dose levels, was 62.2% (28 of 45), with CR in 12 (26.7%), CRI in 15 (33.3%), and PR in 1 (2.2%). Four subjects (8.9%) were reported to have morphologic leukemia-free state (less than 5% blasts in bone marrow aspirate sample with at least 200 nucleated cells) after completion of Cycle 1. Eight

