Once safety of the MTD has been established, any patients still on study at a dose lower than MTD can be dose escalated up to MTD. Patients treated in the lead-in phase at MTD

will be included in the Phase II portion of the study.

The efficacy of the combination will be measured by the overall response rate (ORR), defined as CR (complete remission) + CRp (complete remission with incomplete platelet recovery) + CRi (complete remission with incomplete count recovery) + MLFS within 6 months of treatment initiation among adult patients with refractory/ relapsed AML AND newly diagnosed older patients with AML. ORR and toxicity will be monitored simultaneously using the Bayesian approach of Thall, Simon, Estey (1995, 1996) and the extension by Thall and Sung (1998).

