| | 0.90 | 0.3843 |
| 0.50 | 0.25 | 0.9958 |
| | 0.45 | 0.8852 |
| | 0.60 | 0.7764 |
| | 0.75 | 0.7431 |
| | 0.90 | 0.7385 |

F. Arm 3 Frontline Elderly AML cohort (AZA + VEN + Nivo) (N=30)

Historical data for frontline patients treated with venetoclax and hypomethylating agents (DiNardo CD et al, Blood. 2019 Jan 3;133(1):7-17); Pollyea D et al ASH 2018 Oral presentation Abstract 285.: full PowerPoint attached as Appendix) show ORR of 66%. It is expected for the current trial that the

Nivolumab and azacytidine

three-drug combination will improve the ORR by 15-20% while the toxicity rate is maintained at or below 30%. A sample size of 30 patients ensures that, if the trial is not terminated early, a posterior 90% credible interval for ORR will have width of 0.28 at most, under the assumption of a 80% of ORR. The prior probabilities of ORR and toxicity for the experimental regimen are modeled by beta distributions (*Beta* (1.2, 0.8) and *Beta* (0.6, 1.4), respectively. Denoting the historical proportion of overall response rate and toxicity rate by $\{p(\text{ORR}, H) = 0.60, p(\text{TOX}, H) = 0.30\}$, the following decision criteria will be applied:

- 1) Stop if $\text{Prob}\{p(\text{ORR}, H) + \delta_{\text{OR}} > p(\text{ORR}, E) \mid \text{data}\} > 0.95$, where $\delta_{\text{OR}} = 0.2$
- 2) Stop if $\text{Prob}\{p(\text{TOX}, H) + \delta_{\text{TOX}} < p(\text{TOX}, E) \mid \text{data}\} > 0.90$, where $\delta_{\text{TOX}} = 0$

Patients will be monitored in cohorts of 5 according to the following stopping boundaries for overall response and toxicity.

| # Patients Evaluated | Stop this cohort if \leq this # ORR | Stop if \geq this # toxicities |
|----------------------|---------------------------------------|-------------------------------------|
| 5 | 0-2 | 4-5 |
| 10 | 0-5 | 6-10 |
| 15 | 0-9 | 8-15 |
| 20 | 0-12 | 10-20 |
| 25 | 0-16 | 12-25 |
| 30 | Always stop with this many patients | Always stop with this many patients |

The operating characteristics are summarized in the following table (based on simulations from 10,000 trials).

| True Toxicity Rate | True ORR Rate | PROB(Stop Early) |
|--------------------|---------------|------------------|
| 0.10 | 0.60 | 0.7956 |
| | 0.70 | 0.4433 |
| | 0.80 | 0.1221 |
| | 0.85 | 0.0441 |
| | 0.90 | 0.0114 |
| 0.20 | 0.60 | 0.7985 |
| | 0.70 | 0.4511 |
| | 0.80 | 0.1344 |
| | 0.85 | 0.0575 |
| | 0.90 | 0.0252 |
| 0.30 | 0.60 | 0.8180 |
| | 0.70 | 0.5041 |
| | 0.80 | 0.2180 |
| | 0.85 | 0.1485 |

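### The 66% benchmark for the Arm 3 frontline cohort is a CR/CRi rate, but the monitored ORR also counts MLFS, so the 0.60 row of the operating characteristics does not represent a regimen with no added benefit

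*Combined protocol and SAP*

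**What the plan says.** Section 11.3 F (Arm 3 frontline, N=30) says that the historical data "show ORR of 66%. It is expected for the current trial that the" three-drug regimen will improve on this by 15 to 20 points. The futility rule then enters a historical ORR of 0.60 and a required gain of 0.20, so its bar is 0.80. In the operating-characteristics table, the row "0.10 | 0.60 | 0.7956" (toxicity, ORR, probability of stopping early) implies about 20% completion at ORR 0.60.

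Section 11.2 defines Arm 3 ORR as CR + CRp + "CRi (complete remission with incomplete count recovery) + MLFS within 6 months of treatment initiation".

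The background gives the same 66% as a different quantity. Section 2.3 E, on the 145-patient update cited in 11.3 F, says "The CR/CRI rate for the entire cohort was 66% with a median duration of CR/CRI of 11.0 months". Section 2.6 (venetoclax drug summary) lists the CR/CRi rate for that study ("given venetoclax plus azacitidine or decitabine) was 66" percent), and section 2.6 (rationale, Arm 3) again reports 66% as CR/CRi.

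The only frontline MLFS figure is in the section 2.6 overview of study M14-358, from an earlier cut of 45 patients: 12 CR, 15 CRi and 1 PR, and then "Four subjects (8.9%) were reported to have morphologic leukemia-free state" after cycle 1.

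**The concern.** Under sections 8.1.2 and 8.1.3, CRp already falls within CRi, because CRi allows a platelet count below the CR limit. The category that Arm 3 ORR adds to CR/CRi is therefore MLFS. An MLFS response counts for the triplet but not for the history it is compared with, and nothing in the documents reconciles the two.

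This matters because the cohort is single-arm. The primary analysis estimates ORR with a 95% confidence interval and sets no final success threshold, so comparison with history is the only efficacy yardstick, and the futility rule is the only formal efficacy protection. If the backbone alone gives more than 66% on the Arm 3 definition, the 0.80 bar asks for a smaller gain than the stated 15 to 20 points. An observed ORR in the mid-70s could then be credited to nivolumab.

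**Working it through.** **Inputs (section 11.3 F).** Looks at n = 5, 10, 15, 20, 25. Stop for futility at ≤ 2, 5, 9, 12, 16 responses. Stop for toxicity at ≥ 4, 6, 8, 10, 12 events. Prior for ORR Beta(1.2, 0.8), bar 0.80, cutoff 0.95.

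**Boundary check.** Stopping when P(p < 0.80 | Beta(1.2 + x, 0.8 + n − x)) > 0.95 gives 2, 5, 9, 12, 16, as printed. The toxicity limits are used as printed.

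**Formula.** With independent Binomial(5, ·) increments between looks and response independent of toxicity:

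P(complete) = P(x₅>2, x₁₀>5, x₁₅>9, x₂₀>12, x₂₅>16) × P(y₅<4, y₁₀<6, y₁₅<8, y₂₀<10, y₂₅<12).

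**The plan's own figures.** At toxicity 0.10, P(stop early) is 1 − 0.2044 = 0.7956 at ORR 0.60, 1 − 0.5567 = 0.4433 at 0.70 and 1 − 0.8779 = 0.1221 at 0.80. All 25 printed entries are reproduced to four decimals.

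**Historical rate on the Arm 3 definition.**
- Earlier cut: CR/CRi = (12 + 15)/45 = 27/45 = 60.0%. With MLFS, at most (12 + 15 + 4)/45 = 31/45 = 68.9%. PR is left out because Arm 3 ORR does not count it.
- 145-patient update: CR/CRi = 66%, with no MLFS rate given. If MLFS adds 0 to 4/45 = 8.9 points, the range is 66% to 74.9%.

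**Probability of completing accrual**

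| True ORR | What it represents | Tox 0.10 | Tox 0.20 | Tox 0.30 |
|---|---|---|---|---|
| 0.60 | Value in the rule; 27/45 CR/CRi | 20% | 20% | 18% |
| 0.66 | 66%, no MLFS added | 40% | 40% | 36% |
| 0.689 | 31/45, earlier cut with MLFS | 51% | 51% | 46% |
| 0.70 | Printed row | 56% | 55% | 50% |
| 0.749 | 66% + 8.9 points | 74% | 73% | 66% |
| 0.80 | Futility bar | 88% | 87% | 78% |

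Intermediate values at toxicity 0.10: MLFS adding 3 points (0.69) gives 52%, and 5.1 points (0.711) gives 60%.

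**Separating the two effects (toxicity 0.10).** Moving from 0.60 to 0.66 takes completion from 20% to 40%; this is the mismatch between the cited rate and the rule's input, not the definition. The definition effect is measured on one base at a time: from 40% to at most 74% on the 66% base, and from 20% to at most 51% on the 27/45 base.

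**Distance to the bar.** 80 − 66 = 14 points with no MLFS added; 80 − 74.9 = about 5 points at the upper end.

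**The case against.** The strongest objection concerns size and attribution. A reader might infer that counting MLFS by itself moves completion from 20% to somewhere between 51% and 74%. The documents do not support that. The 51% starts from the 45-patient cut and the 74% from the 145-patient update, so the two ends have different bases. The first 20 points of the path to 74% come from the separate 0.60-versus-0.66 inconsistency.

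The MLFS increment is also uncertain. It is four patients, recorded after cycle 1, across three venetoclax dose levels and both hypomethylating agents. It is tempting to treat 28 responders + 4 MLFS + 8 resistant = 40 of 45 as proof that the groups are disjoint. The sum is compatible with that but does not prove it: a patient with MLFS after cycle 1 could later be counted as CRi. Even 31/45 is therefore an upper limit, and some MLFS cases may already sit within the later 66%. The salvage series in section 2.3 E, where MLFS contributes 4/43 and 4/33, concern relapsed or refractory disease and cannot settle the frontline figure.

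Three further points stand. The table is not miscalculated, and its printed 0.70 row already shows 56% completion. Completing accrual is not a positive result. Counted responses may also be lowered at the looks, because expansion summaries begin after 3 months of treatment while ORR runs to 6 months, and in the final analysis, because dropouts count as failures.

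None of this removes the labelling error or makes 0.60 the right row for no added benefit.

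**Conclusion.** The point holds in a bounded form. The 66% is a CR/CRi rate presented as an ORR, and the Arm 3 endpoint is broader by MLFS. The 15 to 20 point target and the benchmark are on a stricter scale than the responses being counted.

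On the cited 66% base, a regimen adding nothing to the backbone completes accrual 40% of the time at toxicity 0.10 if MLFS adds nothing, and up to about 74% if it adds 8.9 points. At toxicity 0.30 the range is 36% to 66%. Within the earlier cut alone, completion moves from 20% to at most 51% at toxicity 0.10. These figures assume the printed boundaries, independence of response and toxicity, and an MLFS increment between 0 and 8.9 points; the upper end also assumes no overlap with CR/CRi and that the increment carries over to the 145 patients.

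It does not follow that the operating characteristics are wrong for their inputs, or that the plan declares efficacy when the cohort fills.

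**What to change.** In section 11.3 F:

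1. Call the 66% a CR/CRi rate.
2. State the historical rate on the Arm 3 definition as a range, about 66–75%, and give the MLFS assumption behind the upper end.
3. Add operating-characteristics rows at ORR 0.66 and 0.75 (40% and 74% completion at toxicity 0.10) beside the printed 0.70 row.
4. Make any comparison with 66% on CR + CRp + CRi with its 95% confidence interval, reported beside the MLFS-inclusive ORR.

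This costs wording and two rows. Section 8.1 already defines the categories separately, so no extra patients or assessments are needed. The downside is that the stated futility protection will look less favourable.

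Moving the futility boundary itself to CR/CRi is optional and not free. With the 0.80 bar kept, a regimen whose MLFS-inclusive ORR is 0.80 would have CR/CRi of about 0.80 − 0.089 = 0.711 on the same assumption. Its completion at toxicity 0.10 would fall from about 88% to about 60%, and the monitored endpoint would differ from the primary one.
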